## Part A.4. Questions Common to All Studies

*For all questions, if the study involves only secondary data analysis, focus on your proposed design, methods and procedures, and not those of the original study that produced the data you plan to use.*

**A.4.1. Brief Summary.** Provide a *brief* non-technical description of the study, which will be used in IRB documentation as a description of the study. Typical summaries are 50-100 words. *Please reply to each item below, retaining the subheading labels already in place, so that reviewers can readily identify the content.*

**Purpose:** Advanced age and common genetic polymorphism of the antioxidant enzyme glutathione-s-transferase M1 (GSTM1) appear to confer susceptibility to ambient particulate matter (PM). This study will compare responses to PM exposure in older volunteers with GSTM1 null and sufficient genotypes.

**Participants:** 30 healthy 50-75 yo subjects.

**Procedures (methods):** Subjects will be placed on a diet restricted of omega and oleic fatty acids for approximately 42 days prior to undergoing sequential exposures to air (control) and concentrated ambient PM (CAP) for 2 hr. Pulmonary, vascular and cardiac function will be evaluated pre, immediately post and 18 hr post exposure.

**A.4.2. Purpose and Rationale.** Provide a summary of the background information, state the research question(s), and tell why the study is needed. If a complete rationale and literature review are in an accompanying grant application or other type of proposal, only provide a brief summary here. If there is no proposal, provide a more extensive rationale and literature review, including references.

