- Because of reported cardioprotective effects of red wine, subjects will be prohibited from drinking red for 6 weeks prior to their first exposure.
- Subjects who are currently smoking or have smoking history within 1 year of study (defined as more than one pack of cigarettes in the past year) or smoked more than 5 pack-years in lifetime.
- Because the exposures use a facemask that could trigger headaches in sensitive individuals, subjects who suffer from migraines will be excluded from participation.

Use of other medications will be evaluated on a case-by-case basis. There is the potential that an individual's current medication use will preclude them from participating in the study at the current time, but they may be reassessed and potentially rescheduled for participation at a later time.

**A.4.5. Full description of the study design, methods and procedures.** Describe the research study. Discuss the study design; study procedures; sequential description of what subjects will be asked to do; assignment of subjects to various arms of the study if applicable; doses; frequency and route of administration of medication and other medical treatment if applicable; how data are to be collected (questionnaire, interview, focus group or specific procedure such as physical examination, venipuncture, etc.). Include information on who will collect data, who will conduct procedures or measurements. Indicate the number and duration of contacts with each subject; outcome measurements; and follow-up procedures. If the study involves medical treatment, distinguish standard care procedures from those that are research. If the study is a clinical trial involving patients as subjects and use of placebo control is involved, provide justification for the use of placebo controls.

Approximately 30 subjects will complete a regimen in which each subject will undergo exposures to clean air and to CAP sequentially on successive days. Each exposure will be 2 hours in duration with the subject at rest in a specialized exposure chamber.

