- **Brachial artery ultrasound.** Brachial artery ultrasound (BAU) to evaluate flow-mediated dilatation will be performed using a 14 MHz imaging probe interfaced with an Ultrasonix SP or Touch Pharma ultrasound machine. The diameter of the brachial artery will be measured at baseline, during reactive hyperemia and after administration of sublingual nitroglycerin. The subject will lie supine, and a pneumatic tourniquet will be placed around the right upper arm proximal to the target artery. Gated baseline images of the brachial artery will be acquired after 15 minutes of supine rest. The pneumatic cuff will then be inflated to a pressure of 200 mm Hg for 5 minutes, and increased flow will be induced by sudden cuff deflation. A second scan will be performed following deflation. The subject will rest another 10 minutes and a third ultrasound scan will be performed. Sublingual nitroglycerin (~0.4 mg) will be administered, followed in three to four minutes by the final ultrasound study. Subjects will then rest quietly for 5 minutes. Images of the brachial artery will be acquired and stored on a personal computer, and subsequently analyzed using a semi-automated offline quantification system.
- **Pulmonary function:** will be measured by spirometry, including measurement of single breath CO diffusing capacity ( $D_LCO$ ). Cardiac output ( $Q_c$  or pulmonary capillary flow) will be simultaneously measured from the uptake of inhaled acetylene gas during the same single breath procedure.
- **Blood sampling:** approximately 46.2 ml of blood will be collected pre-exposure in the study.

- *Symptom questionnaire* before and after exposure may be collected.
- **Blood Pressure Monitor:** An ambulatory blood pressure monitoring device will be placed on the subject's arm and begin collecting readings. Subjects will wear the blood pressure monitor and cuff for the rest of the day after leaving the facility but will be instructed to remove it before going to bed.

**Exposure:** All exposures will be carried out at the EPA Human Studies Facility on the UNC campus. Subjects will enter an exposure chamber for the 2-hour exposure to clean air. The next day they will undergo exposure to fine/ultrafine CAP for 2 hours. The CAP exposure day may be rescheduled if the particulate concentrations are too low on the scheduled day.

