## 2.0 TASK 1 - SYSTEM MAINTENANCE AND OPERATION

The following paragraphs describe the operational requirements of equipment and systems maintained by TRC and utilized in support of this research study.

Up to 200 test subjects aged 50 – 75 will be recruited to participate in this study, with the goal of completing 30. TRC will monitor the schedule maintained by the subject recruitment contractor (Westat) to determine when to prepare study areas for CAPTAIN activities.

Screening and training periods will precede the exposures. At the training period, subjects will be instructed in day-of-exposure activities, and baseline spirometry, diffusion limited uptake of CO (DLCO), and resting minute ventilation measurements will be obtained. In addition, during the training session, the PI will be responsible for determining the size of face mask required for the subject, and measuring the subject's nose/mouth position while seated in the chamber. A measuring system is available inside and outside Chamber AC89 to enable the PI to determine this vertical position, and forms will be available in a notebook at the console to record the measurement. TRC must make all necessary adjustments prior to starting the aerosol concentrator, which is approximately three hours prior to the scheduled exposure.

Exposures will be conducted in the aerosol exposure chambers located in Room 89, with subjects seated during the entire exposure. Each subject will undergo two two-hour exposures. The first exposure (Tuesday) will be clean air in Chamber PC89. The clean air presented to the subject will be medical grade air that has been humidified to 50 ±10% RH. The second exposure (Wednesday) will be concentrated fine and ultrafine particles in Chamber AC89. Both

clean air and concentrated particles will be presented to the subject through a face mask. Particle exposure sessions can begin no earlier than 10:00 a.m.

On particle exposure days, the TRC Pollutant Control System (PCS) operators will monitor chamber particulate measurements prior to the exposure. If chamber particulate measurements are estimated to be less than  $50\mu\text{g}/\text{m}^3$ , TRC will inform the PI, who will determine whether to run or reschedule the exposure.

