## APPENDIX B

## CAPTAIN EQUIPMENT AND CONFIGURATION

## Study Summary

Number of subjects:	200 recruited/30 complete
Locations:	Chamber AC89, Chamber PC89, Test Room TB87, Medical Station
Exposures per subject:	Two 2-hour exposures using face mask – first to clean air; second to concentrated fine/ultrafine particles (preferably $>50 \mu\text{g}/\text{m}^3$ )
Study blind status:	N/A

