## TRC-Maintained Biomedical Equipment Requirements

Equipment	Room TB87	Chamber AC89	Chamber PC89	Medical Station
Plethysmograph	✓			
Minute ventilation	✓			
Telemetry ECG	✓	✓	✓	✓
Holter monitor				✓
Pulse oximeter		✓	✓	✓
Ambulatory BP monitor				✓
Symptom questionnaire	✓			✓

Shutdown concentration reflects instrument readings, not actual subject exposure conditions. Manual shutdown occurs after confirming that concentrations exceed limits for six consecutive minutes. See text for details.

Controlled during particle exposures only; monitored during clean air exposures. Note that dilution point is determined immediately prior to exposure based on relative accuracy of DataRAM™ to TEOM® measurements. See text for details.

Percentage above dilution point

Not monitored during clean air exposures.

Controlled during clean air exposures only; monitored during particle exposures.

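### Air always precedes CAP, on a different day and in a different chamber, so the CAP effect within a genotype cannot be separated from day, order and chamber

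*Protocol*

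**What the plan says.** Section A.4.5 of the protocol states that "each subject will undergo exposures to clean air and to CAP sequentially on successive days". Its Exposure paragraph puts the clean-air session first and continues: "The next day they will undergo exposure to fine/ultrafine CAP for 2 hours". The one stated exception to the one-day interval is that "The CAP exposure day may be rescheduled if the particulate concentrations are too low on the scheduled day"; air still comes first.

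Section 2.0 of the Protocol Operations Plan ties each exposure to a weekday and a chamber: "The first exposure (Tuesday) will be clean air in Chamber PC89", and "The second exposure (Wednesday) will be concentrated fine and ultrafine particles in Chamber AC89". The Study Summary in Appendix B repeats the order, "first to clean air; second to concentrated fine/ultrafine particles", and gives blind status as not applicable. The air session uses humidified medical-grade air. The humidity footnote in Appendix B reads: "Controlled during clean air exposures only; monitored during particle exposures".

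A.4.1 says function is to be "evaluated pre, immediately post and 18 hr post exposure". The 18 h visit in A.4.5 and in Appendix A follows the particle exposure only, and the blood-draw and visit tables show one follow-up, after the second exposure.

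On inference, A.4.1 and A.4.2 give the purpose as comparing PM responses between GSTM1 genotypes. A.4.8 states a different hypothesis, namely that CAP harms the cardiovascular system in older GSTM1 null volunteers. It plans ANOVA and rank sum tests on pre- and post-exposure data.

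**The concern.** A hypothesis about what CAP causes within one genotype rests on comparing the CAP session with the air session. Those sessions differ in more than particles: in weekday, order, chamber, air source and humidity control. By CAP check-in each subject has also given 2 × 46.2 = 92.4 ml of blood and had two brachial ultrasound studies with cuff occlusion and nitroglycerin.

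Because these differences are the same for every subject, a day, period or chamber term cannot be estimated alongside exposure. This is fixed by the design, so a statistical analysis plan cannot repair it. At stake is whether a positive result could be attributed to CAP at all. Adding subjects does not help, since it only makes a non-CAP difference easier to detect.

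**Working it through.** **1. The plan's own sample size.** Inputs from A.4.8: difference 10%, SD 9%, power 0.8, α 0.05 (two-sided assumed), N = 15.
- Two means, normal approximation: 2 × (1.960 + 0.842)² × 9² / 10² = 12.7, so 13 per group. The two-sample t-test gives 14 per group.
- Paired t-test, SD of the difference 9: n = 9.
- Paired t-test, SD of the difference 9 × √2 = 12.73: n = 15, power 0.808.

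The figure reproduces, so sample size is not the problem. A.4.8 does not say whether 9% is the SD of a single reading or of a within-subject difference, so both 9 and 12.73 are carried as the SD of the difference.

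**2. What the CAP-minus-air contrast estimates.** Let D be a subject's pre-to-post change on the CAP day minus that on the air day. A constant shift in level on day 2 enters both day-2 readings and drops out of D. A simulation with a 5-point shift in both day-2 readings, n = 30 and no CAP effect gave p<0.05 in about 5% of runs, as it should. What remains is

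E(D) = τ + δ,

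where τ is the CAP effect and δ collects the chamber effect, expectation and habituation, and any day-specific pre-to-post response. With one fixed order, τ and δ cannot be told apart.

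**3. Size if τ = 0 (δ is assumed; the documents give no value).** One-sample t-test on D, n = 30, 29 df, critical value 2.045, noncentrality δ√30 / SD.

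| δ (points) | SD 9: noncentrality, P(p<0.05) | SD 12.73: noncentrality, P(p<0.05) |
|---|---|---|
| 2.5 | 1.52, 31% | 1.08, 18% |
| 5 | 3.04, 84% | 2.15, 55% |
| 10 | 6.09, >99% | 4.30, 99% |

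A simulation of 20,000 runs agrees. With SD 9 and δ = 5 the rate is 52% at n = 15 and 84% at n = 30, so it rises with sample size.

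**4. The genotype contrast.** Null minus sufficient gives (τ_null − τ_suff) + (δ_null − δ_suff). The second bracket vanishes only if δ is the same in both genotypes. With 40% of 30 null, the groups are 12 and 18. For a 10-point difference, SE = SD × √(1/12 + 1/18).
- SD 9: SE 3.35, noncentrality 2.98, power 82%.
- SD 12.73: SE 4.74, noncentrality 2.11, power 53%.

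**5. Late outcomes.** With equal start times, a 2 h exposure and check-in 2:15 before exposure (Appendix A), CAP-day check-in falls 24 − 2 − 2.25 = 19.75 h after air ends. For measures other than Holter HRV, the CAP-day pre-exposure reading is the only late post-air value, and it is also the CAP baseline.

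**6. Randomised order, for comparison.** With 15 subjects per sequence and a period term, the simulated false-positive rate is about 5% for all the shifts above when the shift follows the day. Power for a 10-point CAP effect is >99.9% (SD 9) or 98.6% (SD 12.73) at n = 30. A chamber effect would remain while each exposure keeps its own chamber.

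**The case against.** The strongest reply is that the main purpose survives. A.4.1 and A.4.2 name the genotype comparison, A.4.8 justifies 30 subjects by it, and a day or chamber effect common to both genotypes cancels there. This stands, and it limits the point to the CAP main effect, the within-genotype CAP effects and the late changes. It does not rescue the hypothesis in A.4.8, which is about CAP in null subjects.

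Air-first also avoids particle carry-over into the control session. That is a fair defence of the order, although the protocol does not offer it, and it does not make day and exposure separable.

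A reader might infer more than the documents support:
- *Any day-2 shift is counted as a CAP effect.* It is not. Each day has its own pre-exposure readings, and a stable level shift cancels in the changes.
- *Nothing is recorded 18 h after air.* A.4.5 keeps the Holter on for about 48 hours, and section 2.0 has it running for 18 hours after the exposures. Post-air HRV at 18 h is therefore recorded when the schedule holds, although the Outcomes section does not designate that epoch.
- *Rescheduling CAP always destroys the late post-air value.* The concentrator starts two to three hours before chamber entry and check-in is at -2:15, so pre-exposure measures may already be under way when low levels are seen. The value may be lost, but need not be.
- *Image and Holter readers are known to be unmasked.* The not-applicable entry stands in a contractor's operations plan, and that contractor has no responsibility for the ultrasound system. The protocol simply describes no masking.
- *The 18 h analysis carries a particular loss of precision.* The protocol specifies no such contrast, so this cannot be charged to it.

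**Conclusion.** The point holds as a limit on what the trial can conclude. Exposure is completely aliased with day, order and chamber, so the CAP main effect and the CAP effect within GSTM1 null or sufficient subjects are not identifiable. The genotype by (CAP minus air) contrast is interpretable on the assumption that the non-cancelling effects are equal in the two genotypes.

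The possible error equals the whole non-cancelling shift. Over assumed shifts of 2.5 to 10 points, the chance of a false CAP finding at n = 30 runs from 18% to more than 99%, depending on the shift and on whether the SD of the difference is 9 or 12.7. These figures illustrate the exposure to bias. They do not show that such a shift exists.

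For outcomes other than Holter HRV, the only late post-air reading doubles as the CAP baseline. It falls about 20 h after air if start times match, and it may no longer lie near 18 h if CAP is rescheduled.

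**What to change.** 1. In A.4.8, name genotype by (CAP-day change minus air-day change) as the confirmatory inference. State that the CAP main effect, the within-genotype CAP effects and the 18 h changes cannot be separated from day, order and chamber, and state the equal-effects assumption on which the genotype contrast relies.
2. Code the stored brachial ultrasound images and Holter files so that the offline analysts see neither exposure nor genotype.

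The cost of the first is a narrower claim, with power of about 82% (SD of difference 9) or 53% (SD 12.7) for a 10-point genotype difference with 12 null and 18 sufficient subjects. The second costs only file handling.

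Randomising the order within genotype, with the sessions in separate weeks and a period term in the model, would remove order and day bias without a larger sample. It needs extra visits, including an 18 h return after air if that control is wanted, and it leaves the chamber effect in place while each exposure keeps its own chamber. It is an option for the sponsor, not the required change.

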#### **OUTCOMES:**

**Pulmonary Function** will be measured before and after exposure. Subjects who have recent abdominal and/or eye surgery or any type of hernia will not be tested for pulmonary function. Subjects will perform spirometry and single breath diffusing capacity (DLCO) on a Sensor Medic Vmax pulmonary function system according to the standard procedure published by the American Thoracic Society. In addition, regional DLCO and pulmonary capillary blood flow (Qc) will be obtained by the intrabreath technique using the same system.

**Heart Rate Variability (HRV)** data will be gathered for 24 hours using a Holter monitor. Specific 10 minute epochs to be analyzed for frequency domain variables include times immediately prior to exposure, immediately following exposure, and approximately 24 hours after exposure. Both time and frequency domain variables will be analyzed, as will abnormal responses (e.g. premature atrial complex, premature ventricular contractions, bradycardia, and tachycardia).

**Flow-Mediated Dilatation (brachial artery ultrasound).** Changes in diameter of arteries caused by reactive hyperemia (endothelium-dependent vasodilatation) and by administration of sublingual nitroglycerin, typically 0.4 mg, (endothelium-independent vasodilatation) will be expressed as a percent change in diameter relative to resting baseline values.

**Peripheral Venous Blood Sample.** Approximately 50 ml of venous blood will be drawn before, immediately after (within 1 hr after exposure ends), and approximately 18 hrs after exposure (Please refer to Table 1 in this section). The site will be prepared with isopropyl alcohol and a tourniquet is applied. Blood is drawn from an antecubital or other appropriate vein. Endpoint measurements will include, but are not limited to the following: blood lipid omega-3 fatty acid levels, biomarkers for specific and non-specific immune responses, coagulation factors, vasoactive factors, and soluble components of PM (e.g. transition metals).

Genotype Screen	Air Exposure	Ozone-Exposure	Follow-up	TOTAL
20	46.2/46.2	46.2/46.2	46.2	251 ml

Table 1. Blood Draws

Our primary endpoints will be HRV measurement, pulmonary function and peripheral venous blood markers. Our secondary endpoints will be arterial wall function and pulmonary function measurements.

**A.4.6. Benefits to subjects and/or society.** Describe any potential for direct benefit to individual subjects, as well as the benefit to society based on scientific knowledge to be gained; these should be clearly distinguished. Consider the nature, magnitude, and likelihood of any direct benefit to subjects. If there is no direct benefit to the individual subject, say so here and in the consent form (if there is a consent form). Do not list monetary payment or other compensation as a benefit.

Subjects will receive no direct benefit from participating in this study other than receiving a medical examination, including blood work, brachial artery ultrasound, spirometry, and an ECG. Subjects will have full access to these records. They will also gain knowledge about their responsiveness to ambient particulate matter.

For society, this study will provide new information on the effects of ambient particulate matter on lung function, inflammation, and the cardiovascular system. Data from this study will help the US EPA better understand the components of air pollution that are responsible for increasing morbidity and mortality of cardiopulmonary fatality so that National Ambient Air Quality Standards and motor vehicle emission standards can be properly set. Findings from this study will also become the potential to contribute to devising effective strategies aimed at the protection of the public from the untoward effects of these pollutants.

**A.4.7. Full description of risks and measures to minimize risks.** Include risk of psychosocial harm (e.g., emotional distress, embarrassment, breach of confidentiality), economic harm (e.g., loss of employment or insurability, loss of professional standing or reputation, loss of standing within the community) and legal jeopardy (e.g., disclosure of illegal activity or negligence), as well as known side effects of study medication, if applicable, and risk of pain and physical injury. Describe what will be done to minimize these risks. Describe procedures for follow-up, when necessary, such as when subjects are found to be in need of medical or psychological referral. If there is no direct interaction with subjects, and risk is limited to breach of confidentiality (e.g., for existing data), state this.

**General measures to minimize the risks:** Medical screening of the potential subjects is designed to exclude those that may be at risk from the study procedures. A qualified physician is available in the building whenever a subject is undergoing any procedure. The exposure will be terminated for any rapid change in symptoms, tachycardia and/or arrhythmia, decline in arterial oxygen saturation, or for any distress of concern to the volunteer or the console operator. Medical staff and medication are immediately available (within the building) should it be necessary. HSF has a fully stocked medical station and the University of North Carolina Hospital is a short distance from the HSF. On days after exposure subjects will be urged to contact the medical station should they experience any of the following symptoms: epistaxis, persistent cough, chest pain, dyspnea, wheezing, hoarseness, or sore throat. Risks associated with specific study procedures are as follows:

- **Pulmonary function tests** (spirometry) are standard non-invasive techniques that are commonly used in studies of pulmonary function on populations of all ages and entail little or no risk to the subject. The intrabreath technique uses a single breath of 0.3 % acetylene uptake for measurement of pulmonary blood flow (cardiac output). Although large doses of acetylene can cause nausea, vomiting, and headache our subjects will be exposed to a single inhalation of a low

concentration of acetylene for a brief period of time. Thus the risks of these complications to our subjects are extremely low.

- **ECG and heart rate variability** are standard non-invasive techniques commonly used for heart rate and rhythm analysis and entail little or no risk to the subject. There is the possibility that preparation of the skin for electrode placement and removal may cause skin irritation, itching, or soreness in some subjects.

- **Brachial artery ultrasound:** There are no known risks associated with imaging of the brachial artery. However, intermittent brief occlusion of blood flow to the forearm may cause mild discomfort and temporary sensations such as tingling and numbness until the blood pressure cuff is released. Approximately 0.5 % of participants develop painless petechiae in the arm which is examined and these resolve within a few days. Sublingual nitroglycerin used in the brachial artery ultrasound measurement is a potent vasodilator, and may cause headache, flushing, and transient hypotension. These effects are short-lived because the peak plasma concentration occurs within 4 minutes of administration and the plasma half-life is approximately 5 minutes. To minimize the risk of hypotension, the subject will remain lying down for 10 minutes after receiving nitroglycerin. In addition, individuals who may be at risk of excessive blood pressure lowering (i.e. individuals who have baseline systolic blood pressure < 90 mm Hg, or who have obstruction of the left ventricular outflow tract due to aortic stenosis or a dynamic outflow gradient) will be excluded from this study during screening. Allergic reactions to nitroglycerin have been reported, but are rare.

- **Blood Pressure Monitoring.** There is a small chance of bruising as a result of wearing the blood pressure monitoring cuff.

- **Venipuncture** will be done by insertion of the needle and may cause minor discomfort at the site of injection and there is a possibility that a bruise will form which may be painful for 2-3 days. It is possible that the subject may feel lightheaded or even faint due to anxiety about the blood draw. Rarely, a skin infection may occur. To minimize these risks, blood is drawn by trained medical professionals. Subjects are in a semirecumbent position and closely monitored for any signs of faintness, given liquids and food to eat if requested, and only allowed to leave the facility after a 15-minute waiting period to make sure they are stable when in the erect position.

- **CAP Exposure .** The subjects in this study will be exposed to an inhaled particle mass that does not exceed what they would encounter over 24 hours in a typical urban environment on a smoggy day. It is expected that particulate exposure levels will be up to 600 ug/m^3 and the exposure will be terminated if the level exceeds 600 ug/m^3 for greater than 6 minutes. Thus while we cannot completely rule out the possibility of an adverse effect, since we are exposing the volunteers to a particulate exposure burden they would likely encounter if visiting a large city, we feel the risk posed to volunteers is very small. Possible health effects of acute exposures to air pollution particles include chest pain, mild dyspnea, headache, cough, and, wheeze. All of these effects would be expected to resolve spontaneously within hours of exposure cessation. The particulate exposure may possibly cause increased airways inflammation. It is also possible that exposure could uncover a previously unidentified pre-existing cardiac condition that could present a health risk to a subject. During the exposures, subjects will be continuously monitored during the entire exposure by direct observation. A physician on duty in the facility will be available when exposures are occurring. Heart rate, continuous electrocardiogram via telemetry, and SaO2 by pulse oximetry will also be monitored continuously, and blood pressure will be monitored every 15 minutes. Indications for terminating the exposure include significant respiratory distress or dyspnea, chest or angina-like pain, significant cardiac arrhythmias, pallor, or ataxia. Subjects will be aware that they can terminate their exposure for any reason and still

Field Cod

receive compensation for the entire session. The investigators or duty physician will end the exposure if the subject is found to be suffering from any adverse effect. Full resuscitation equipment will be available at all times during exposures and in the event of an emergency, after initial medical assessment, patients will be transported to UNC Hospitals Emergency Department for continued treatment.

- **Confidentiality** Risk of breach of confidentiality is minimal. All subjects will be assigned a study number which will be used for data recording – not the subject’s name. The study number is all that will be entered into computer databases. All paper files that may contain the subject’s name or screening number are secure in the EPA building that has limited access 24 hours/day. Any abnormal medical findings (CBC, ECG, brachial artery ultrasound image, spirometry) will be discussed with the volunteer and the volunteer will be counseled to seek treatment from his/her personal physician if indicated. Samples will be stored at the U.S. EPA HSF. A numeric coding system will be used to ensure that subjects cannot be directly identified from the samples alone.

**A.4.8. Data analysis.** Tell how the qualitative and/or quantitative data will be analyzed. Explain how the sample size is sufficient to achieve the study aims. This might include a formal power calculation or explanation of why a small sample is sufficient (e.g., qualitative research, pilot studies).

To test our hypothesis that CAP causes adverse cardiovascular effects in GSTM1 null older human volunteers, we will measure a number of relevant endpoints, including blood pressure, HRV, brachial arterial blood flow rate, change in blood coagulation factors, platelets, fibrinogen, c-reactive protein, lactate, plasminogen activator inhibitor, ferritin, and  $\alpha$ 1-antitrypsin. In this study, our primary endpoints will be HRV measurement and peripheral venous blood markers. Our secondary endpoints will be endothelial cell function and pulmonary function measurements. Statistical data analyses will consist of ANOVA for continuous variables and rank sum tests for non-continuous variables pre- and post-exposure. A  $p$  value of 0.05 or less will be considered significant.

The sample size was calculated to detect a difference of 10% change in HRV assuming a standard deviation of 9%. Using GraphPad software, an N of 15 was derived using a power of 0.8 and an  $\alpha$  of 0.05. This study will enroll approximately 30 subjects in order to provide sufficient power to all for the examination of differences between GSTM1 null and positive subjects.

The study cohort will be monitored through genetic screening to ensure that individuals with GSTM1 null genotype are represented in a proportion approximately equal to the prevalence in the US population, about 40%.

Based on recently completed studies for subjects with the characteristics sought in this study, the expected screening attrition rate is up to 70%, with a heavy effect of genotype requirement. Post-screening completion rate is up to 50%. Extrapolating from these rates, we can expect a 15% overall completion yield. Therefore, to obtain 30 subjects, we will enroll approximately 200 subjects.

**A.4.9. Will you collect or receive any of the following identifiers?** Does not apply to consent forms.

No  Yes *If yes, check all that apply:*

- a.  Names
- b.  Telephone numbers
- c.  Any elements of dates (other than year) for dates directly related to an individual, including birth date, admission date, discharge date, date of death. For ages over 89: all elements of dates (including year) indicative of such age, except that such ages and elements may be aggregated into a single category of age 90 and older
- d.  Any geographic subdivisions smaller than a State, including street address, city, county, precinct, zip code and their equivalent geocodes, except for the initial three digits of a zip code
- e.  Fax numbers
- f.  Electronic mail addresses
- g.  Social security numbers
- h.  Medical record numbers
- i.  Health plan beneficiary numbers
- j.  Account numbers
- k.  Certificate/license numbers
- l.  Vehicle identifiers and serial numbers (VIN), including license plate numbers
- m.  Device identifiers and serial numbers (e.g., implanted medical device)
- n.  Web universal resource locators (URLs)
- o.  Internet protocol (IP) address numbers
- p.  Biometric identifiers, including finger and voice prints
- q.  Full face photographic images and any comparable images
- r.  Any other unique identifying number, code, or characteristic, other than dummy identifiers that are not derived from actual identifiers and for which the re-identification key is maintained by the health care provider and not disclosed to the researcher

**A.4.10. Identifiers in research data.** Are the identifiers in A.4.9 above linked or maintained with the research data?

X yes - no

**A.4.11. Confidentiality of the data.** Describe procedures for maintaining confidentiality of the data you will collect or will receive. Describe how you will protect the data from access by those not authorized. How will data be transmitted among research personnel? Where relevant, discuss the potential for deductive disclosure (i.e., directly identifying subjects from a combination of indirect IDs).

No personal identifying information will be attached to the samples. No subjects will be identified in any report or publication about this study. Study samples will be stored in a secure room with restricted access. The sample will be prepared and stored indefinitely in a freezer for future testing. Portions of the sample may be shared with researchers at other scientific institutions or sent to outside clinical laboratories for analysis, however, only coded samples will be sent. All medical records generated during this study will be kept in the medical records office at the U.S. EPA Human Studies Facility.

**A.4.12. Data sharing.** With whom will *identifiable* (contains any of the 18 identifiers listed in question A.4.9 above) data be shared outside the immediate research team? For each, explain confidentiality measures. Include data use agreements, if any.

- No one
- Coordinating Center:
- Statisticians:
- Consultants:
- Other researchers:
- Registries:
- Sponsors:
- External labs for additional testing:
- Journals:
- Publicly available dataset:
- Other:

**A.4.13. Data security for storage and transmission.** Please check all that apply.

*For electronic data:*

- Secure network  Password access  Encryption
- Other (describe):
- Portable storage (e.g., laptop computer, flash drive)  
*Describe how data will be protected for any portable device:*

*For hardcopy data (including human biological specimens, CDs, tapes, etc.):*

- Data de-identified by research team (stripped of the 18 identifiers listed in question A.4.9 above)
- Locked suite or office
- Locked cabinet
- Data coded by research team with a master list secured and kept separately
- Other (describe):

**A.4.14. Post-study disposition of identifiable data or human biological materials.** Describe your plans for disposition of data or human biological specimens that are identifiable in any way (directly or via indirect codes) once the study has ended. Describe your plan to destroy identifiers, if you will do so.

Samples will be stored in a repository where only project members of the study will have access to the samples.

